7.4.2 Analysis of Secondary Variables

The secondary efficacy variables will be analyzed using FAS population.

- Time to complete ulcer healing:

Time to complete ulcer healing will be calculated for all subjects from the day of the first study medication applied until the day that original healing of target ulcer is first observed. Subjects who could not achieve complete ulcer healing at the last evaluation time point will be censored (non-healing) at the date of last evaluation. The median time to complete ulcer healing will be estimated by Kaplan-Meier method and two-sided 95% confidence interval will be reported. The log-rank test will be performed for comparing time to complete ulcer healing among two groups.

- Percentage change in ulcer surface area from baseline:

Summary statistics of the measured wound size and the percentage change from baseline will be obtained for each group by observation time point and their changes over time will also be graphically presented.

For the analysis on the ulcer surface area, the percentage change from baseline at each visit will be calculated using the actual wound size. The wound size percentage change will be compared between groups by means of analysis of co-variance (ANCOVA) adjusted with baseline measurement of sizes and baseline Wagner grade.

- Percentage of subjects with a 50% reduction of ulcer surface area:

The proportion of subjects who achieve 50% reduction of wound size from baseline to interim visit will be calculated for two groups and analyzed by a logistic regression model with treatment as factor, and baseline wound size and Wagner grade as covariates.

- Incidence of infection of the target ulcer:

The incidence of infection of the target ulcer will be summarized and tabulated by two treatment groups at the final ulcer assessment. The incidence of infection of target ulcer between two groups will be compared using Fisher's exact test.

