1.4 Rationale for Trial Design

New treatments that improve the number of ulcers that heal and/or speed up healing are urgently needed. The main purpose of our clinical trial is to demonstrate superiority of ON101 vs. Aquacel[®] Hydrofiber[®] in wound healing. Previous studies with ON101 showed that ON101 is associated with wound size reduction and improved healing rate. However, these studies were not adequately powered for wound healing rate as primary endpoint. This comparative study is important because the results may inform the choice in managing the DFU. The proposed study will provide 16 weeks data on wound healing rate in order to demonstrate superior benefits of ON101 compared to Aquacel[®] Hydrofiber[®] dressing on a clinically important outcome. Clinical healing and safety will be compared in diabetic patients with Wagner Grade 1 or 2 DFUs managed with either of two primary treatments: ON101 cream or Aquacel[®] Hydrofiber[®] dressing, both used within similar standard care including appropriate lower extremity off-loading.

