7 STATISTICAL METHODOLOGY

7.1 Sample Size

The recent phase 2 clinical trial was carried out 30 subjects with Wagner-grade-1 chronic diabetic foot ulcers treated with ON101 for up to 12 weeks. The results showed that the incidence of healing by 12 weeks was 50% and the time of 50% subjects reached healing was approximately 10 weeks. Of the 30 subjects, treatment with ON101 for up to 12 weeks resulted in approximately 70% reduction of wound size. The average wound size at baseline was 577 mm² (303 - 1225 mm²), and decrease to 163 mm² for up to 12 weeks of ON101.

Sample size calculation is performed by the superiority test based on the incidence of complete healing of the target ulcer between the two treatment groups within 16 weeks. The ON101 cream will be considered to be effective if the complete healing rate is superior to the corresponding endpoint of the Aquacel[®] Hydrofiber[®] dressing at two-sided 5% significance level. The hypothesized complete healing rate difference between two treatment groups is 20%, assuming the rates are 50% for ON101 cream and 30% for Aquacel[®] Hydrofiber[®] dressing. This study is also planned two interim and 1 final analysis at around 50%, 90%, and 100% of study information, and the futility/superiority of ON101 cream will be assessed using the Lan-DeMets alpha-spending approach with an O'Brien-Fleming boundary.

Under the assumption described above and with a 1:1 randomization ratio of the two groups, a minimal 212 evaluable subjects will be required to achieve at least 80% power to detect a significant difference in complete healing rate using a 2-sided alternative at the 5% nominal significance level. Assuming the non-evaluability rate is 10%, a total of 236 subjects (118 subjects for ON101 cream and 118 subjects for Aquacel[®] Hydrofiber[®] dressing) will be enrolled into this trial.

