7.4 Analysis of Efficacy

7.4.1 Analysis of Primary Variable

The primary efficacy variable is the proportion of subjects whose target ulcer is complete healing. The definition of complete healing for the target ulcer is complete epithelialization which is maintained with no drainage for at least 2 weeks and is confirmed by a blinded independent evaluator.

This will be a multi-center study. It is anticipated that the number of participating centers can be large and the number of subjects enrolled at each center could be small. As a result, the data from all centers will be pooled for statistical analyses.

The hypothesis for the comparison is given as follows:

H_0 : The healing rates on ON101 cream and Aquacel® Hydrofiber® dressing are the same

H_1 : The healing rates on ON101 cream and Aquacel® Hydrofiber® dressing are not the same

The number of percentage of subjects achieving the efficacy endpoints will be summarized by visit and ON101 cream group will be compared to the Aquacel[®] Hydrofiber[®] dressing group with Chi-square test. The logistic regression model with treatment/intervention as fixed factor, and baseline wound size and Wagner grade as covariates will be applied to the primary analysis of primary endpoint. The results of the logistic regression model will be presented in terms of the odd ratio (ON101 cream versus Aquacel[®] Hydrofiber[®] dressing), with p-values and associated 95% confidence intervals of the odds ratio.

The test intervention (ON101 cream) will be concluded to be superior to the control (Aquacel[®] Hydrofiber[®] dressing) in average if the null hypothesis (H_0) is rejected and the odds ratio higher than 1. To reflect the interim analysis, final analyses will be based on a Type I error rate (two-sided) of 0.039611.

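### In the supplied text, the four secondary efficacy endpoints are each tested between groups with no order, gate on the primary, alpha split or descriptive label

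*Combined protocol and SAP*

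**What the plan says.** Section 7.4.2 states: "The secondary efficacy variables will be analyzed using FAS population". It then assigns one method to each endpoint:

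- Time to complete healing: "The log-rank test will be performed for comparing time to complete ulcer healing among two groups".
- Percentage change in ulcer area: "the percentage change from baseline at each visit will be calculated using the actual wound size". The next sentence prescribes an ANCOVA adjusted for baseline size and Wagner grade, and names no visit.
- 50% area reduction: logistic regression, measured from baseline to an interim visit that is not defined.
- Target-ulcer infection: Fisher's exact test at the final ulcer assessment.

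No significance level is attached to any of the four. The primary is handled differently. Section 7.1 sizes the trial on complete healing "at two-sided 5% significance level". Section 7.6.2 sets Lan-DeMets O'Brien-Fleming boundaries for three looks. Section 7.4.1 ties the superiority conclusion to rejection of the primary null hypothesis with an odds ratio above 1, and adds: "To reflect the interim analysis, final analyses will be based on a Type I error rate (two-sided) of 0.039611". Recurrence is called exploratory (sections 2.3.3 and 7.4.3); the four secondaries carry no such label. Section 7.2 defers statistical detail to a separate SAP, which is not in the supplied text.

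**The concern.** The plan controls the error rate of its primary claim carefully and, in the supplied text, says nothing about the error rate of the four secondary tests. It does not say at what level they are read, whether they are read at all if the primary misses, or which level applies if the trial stops at the second interim.

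Section 1.4 makes this more than a formality: "New treatments that improve the number of ulcers that heal and/or speed up healing are urgently needed". Speed of healing is thus presented as a benefit alongside the number healed, and time to healing is the first-listed secondary. If the primary missed narrowly, a small p-value on a secondary could be offered as evidence of efficacy, with no rule fixed in advance for how to read it.

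Two tests also lack a time point: the ANCOVA has no named visit, and the 50% reduction endpoint has an undefined one. Either could be settled after data are seen.

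**Working it through.** **Step 1: the plan's own figures.** The inputs are the boundaries 0.003957, 0.034760 and 0.039611 (section 7.6.2) at 124, 212 and 236 subjects, i.e. information 124/236 = 0.525, 212/236 = 0.898 and 1. Recomputing the Lan-DeMets O'Brien-Fleming boundaries at 0.525, 0.898 and 1 gives 0.003957, 0.034757 and 0.039611. The stated boundaries together give an overall two-sided type I error of 0.0500. The primary is controlled, so the question is confined to the secondaries.

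**Step 2: number of tests.** One test per endpoint gives 4. Visits 3 to 10 (section 5.1.3) are eight visits. If the ANCOVA were run at each, the family would be 8 + 3 = 11.

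**Step 3: independent tests, no true effect on any secondary.** The chance of at least one nominally significant result is 1 − (1 − α)^k.

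- k = 4: 1 − 0.95^4 = 18.5%; 1 − (1 − 0.039611)^4 = 14.9%.
- k = 11: 1 − 0.95^11 = 43.1%; 1 − (1 − 0.039611)^11 = 35.9%.

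The plan states no level for the secondaries. I use 0.05 as the conventional one and 0.039611 as the only final-analysis level given.

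**Step 4: correlated tests.** The documents give no correlations, so a range is assumed. The entries are the probability that the largest |Z| of k equally correlated normal statistics exceeds the two-sided critical value. The row for correlation 0 is the formula above and the rest are simulated.

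| Assumed correlation | 4 tests, 0.05 | 4 tests, 0.039611 | 11 tests, 0.05 | 11 tests, 0.039611 |
|---|---|---|---|---|
| 0 | 18.5% | 14.9% | 43.1% | 35.9% |
| 0.3 | 17.3% | 14.0% | 37.4% | 31.1% |
| 0.5 | 15.6% | 12.6% | 30.4% | 25.2% |
| 0.7 | 13.0% | 10.5% | 22.3% | 18.4% |
| 0.8 | 11.4% | 9.2% | 18.0% | 14.9% |

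**Step 5: a check with the planned tests.** Wound courses were simulated for 236 subjects with no treatment effect (healing 24–33% and infection 10–20%, both assumed), and the log-rank, ANCOVA, logistic and Fisher tests were applied. One test per endpoint gave 14.2–15.2% at 0.05 and 11.2–12.3% at 0.039611. With the ANCOVA at all eight visits the figures were 20–27% and 16–22%. All lie inside the ranges in the table. Fisher's test is conservative here (true size about 3% at a nominal 5%), which pulls the figures down a little.

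**Step 6: direction.** Counting only results that favour ON101, at correlation 0.5, four tests give 7.8% at 0.05 and 6.3% at 0.039611, half of 15.6% and 12.6%. Eleven tests give about 15% and 13%.

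**Step 7: effect of a rule.** With no true effects:

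- A fixed sequence of the four gives 5.0% at 0.05 and about 4.0% at 0.039611.
- A gate on the primary alone gives 0.9–3.0% at 0.05 (assumed correlation 0–0.7). That protection disappears once ON101 truly improves healing, because the gate is then usually open and the four tests behind it are again uncontrolled. An order or alpha split is therefore needed as well.

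**The case against.** The plan makes no confirmatory claim on a secondary. Superiority is concluded from the primary alone, and the sample size and the three boundaries concern healing incidence only. Section 1.4 is background, and the same section names healing rate as the outcome on which superiority is to be shown. All of this stands. A reader might infer that the plan allows efficacy to be declared on a secondary when the primary fails. No section provides for that; the supplied text simply does not say how such a result would be read.

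A reader might also infer that area change is tested at every visit, so that the 11-test figures describe the plan as it stands. They do not. In section 7.4.2 the phrase about each visit belongs to the calculation of percentage change, and the ANCOVA sentence names no visit and does not say the test is repeated. The 11-test figures are conditional on a choice the text leaves open.

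Three further limits stand. The percentages depend on assumed correlations and an assumed per-test level. The two-sided rates count results favouring either arm, so they overstate the chance of a false result for ON101 by about a factor of two. They also do not quantify the narrow-miss case, because they do not condition on the primary result. Finally, the separate SAP may contain a rule; if so, the remedy is to cite it and align section 7.4.2.

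What the objection leaves untouched is that four comparative tests are planned with neither error control nor a descriptive label in the supplied text.

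**Conclusion.** The point holds as an inexpensive improvement to the secondary analyses. It is not a threat to the primary conclusion, which is controlled at 5%. With one test per endpoint and no true effect on any secondary, the chance of at least one nominally significant result in either direction is about 9–19%, and about half that in favour of ON101. The range covers per-test levels of 0.039611 and 0.05 and assumed correlations of 0 to 0.8. If the ANCOVA were run at all eight comparative-period visits, the two-sided rate would be about 15–43% over the same assumptions. The finding is limited to the supplied text.

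**What to change.** Amend section 7.4.2, and the SAP to match, before second-interim data are seen:

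1. Test secondaries only if the primary null hypothesis is rejected with an odds ratio above 1.
2. Test them in a fixed sequence chosen by the sponsor. One example is time to complete healing; percentage area change at the end of the comparison period; 50% area reduction at one named visit, replacing the undefined interim visit; then target-ulcer infection.
3. Test each at the two-sided level in force at the look where the primary is rejected: 0.034760 at the second interim, 0.039611 at the final.
4. Stop at the first non-significant result. Later p-values, and all by-visit comparisons, are descriptive.

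If no secondary claims are wanted, one sentence labelling all secondary p-values descriptive is enough. The ANCOVA visit and the 50% reduction visit should be named in either case.

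The cost is a documented protocol amendment with the approvals in section 8.3.3. It needs no new data, subjects or procedures and does not change the primary test. The statistical downside of the sequence is that an early non-significant endpoint blocks formal claims on those after it, so the order should reflect the sponsor's priorities.

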Standard ulcer care	X	X	X	X	X	X	X	X	X	X	X	X	X	X
Demographics	X													
Inclusion/Exclusion criteria	X	X												
Disease status	X	X												
Pregnancy test	X													
Physical examination	X	X	X	X	X	X	X	X	X	X	X	X	X	X
Ulcer assessment	X	X	X	X	X	X	X	X	X	X	X	X	X	X
Photography	X	X	X	X	X	X	X	X	X	X	X	X	X	X
12 Lead ECG	X									X				X
X-Rays	X													
Vital signs	X	X	X	X	X	X	X	X	X	X	X	X	X	X
Laboratory tests	X			X		X		X		X				X
Medical history	X	X												
Concomitant medication	X	X	X	X	X	X	X	X	X	X	X	X	X	X
Assessment of adverse events		X	X	X	X	X	X	X	X	X	X	X	X	X

* : Day 1 should normally be the day of first treatment intake. The day before should normally be Day -1 and there is no Day 0.

This approach is in accordance with CDISC.

: Subject may proceed to Visit 2 as soon as Visit 1 procedures are completed, that means the day of Visit 1 could be same as Visit 2.

& : Visit 10 indicates as the end of study treatment or prematurely discontinuation of study treatment.

@: During the follow-up period, Aquacel[®] Hydrofiber[®] dressing will be applied for subjects who have unhealed or with recurrence wound.

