2.2 Study Design and Dose Rationale

2.2.1 Study Design and Rationale

This trial is designed as a randomized, evaluator blinded, active-controlled, multi-center study comparing the efficacy and safety of ON101 cream and Aquacel® Hydrofiber® dressing in the treatment of diabetic foot ulcers. An independent evaluators who blinded to subjects' treatment will evaluate whether the wound has healed, defined as epithelialization wound. Subject with Type 1 or 2 diabetes mellitus (DM) and with Wagner Grade 1 or 2 diabetic foot ulcer (DFU) of neuropathic or neuro-ischemic etiology will be included in this study. If there is more than one ulcer on the foot, the most severity then largest ulcer that confirmed to the inclusion/exclusion criteria will be selected for study evaluation. Eligible subjects will be randomized to receive either ON101 cream or Aquacel® Hydrofiber® dressing in a 1:1 allocation. The study treatment will be applied to the selected ulcer for a maximum period of 16 weeks, until the wound/ulcer closure (wound size of 0) for two consecutive visits at least 2 weeks apart, or until the subject exited the study as treatment failure. After that, all subjects regardless of wound healing at the end of comparison period will be followed for 12 weeks to investigate durability. During the follow-up period, Aquacel® Hydrofiber® will be applied for subjects who have unhealed or with recurrence wound. Each target ulcer with wound photographs for blind assessment will be monitored at each scheduled visit.

Two interim analyses will be conducted at around 50% and 90% of study information; the final analysis will be conducted at the end of the study. The futility/superiority of ON101 cream will be assessed using the Lan-DeMets method with O'Brien-Fleming spending boundaries.

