2.3 Variables

2.3.1 Primary Variable

The primary variable is the number of target ulcers healed in each group within 16 weeks. The primary efficacy outcome is the comparison of the incidence of complete healing of the target ulcer between the two treatment groups at the end of treatment.

For the purpose of this study a complete healing will be defined as complete epithelialization which is maintained with no drainage for at least 2 weeks and is confirmed by a blinded independent evaluator.

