5.1.3 Comparative Period

(Visit 3-Visit 10: Day 15 to Day 113)

The following procedures will be performed in this period:

- Apply test medication or comparative intervention

If complete wound healing by the judgment of independent reviewer happens before Visit 10, the applied test medication (ON101 cream) or comparative intervention (Aquacel® Hydrofiber® dressing) will be stopped at next scheduled visit which will be deemed as V10.

If the wound is unhealed at Visit 10, only Aquacel® Hydrofiber® dressing will be applied.

- Perform physical examinations and obtain vital signs
- Perform laboratory tests including hematology and biochemistry at Visit 4, Visit 6, Visit 8, Visit 10 and at the visit of early permanent discontinuation of study treatment
- 12 Lead ECG examination will be performed at Visit 10 or at the visit of prematurely discontinuation of study treatment
- Perform assessment of foot ulcer status and photography
- Standard ulcer care
- Perform assessment of adverse events
- Record concomitant medication

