5.1.4 Follow-up Period

(Visit 11-Visit 14: Day 127 to Day 197)

The following procedures will be performed in this period:

- Apply Aquacel® Hydrofiber® dressing to the subjects whose wounds are unhealed or recurrent
- Perform physical examinations and obtain vital signs

- Laboratory tests including hematology and biochemistry will be performed at Visit 14 (Week 28) or Visit of early permanent discontinuation during the follow-up period
- 12 Lead ECG examination will be performed at visit 14 (Week 28) or visit of early permanent discontinuation during the follow-up period
- Perform assessment of foot ulcer status and photography
- Standard ulcer care
- Perform assessment of adverse events
- Record concomitant medication

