5.4 Efficacy Assessment

The efficacy assessment is based on the subject's wound size. It will be conducted at clinic by digital planimetry method at baseline and every 2 weeks after study intervention until wound closure (wound size of 0) has confirmed 2 weeks apart, or until the study subject exited the study as lack of efficacy satisfactory.

The digital planimetry method involves applying a two-layer transparent acetate over the wound and tracing the perimeter with a permanent pen. The contact layer is then discarded into clinical waste and the top layer stored within the subject notes. The top layer is placed on a digital tablet, and the border is re-traced using a stylus. The underlying sensor then calculates the wound area.

For the purpose of this study a complete healing will be defined as complete epithelialization which is maintained with no drainage for at least 2 weeks and is confirmed by a blinded independent evaluator. At each clinic visit after study intervention, digital photographs should be taken of study wound after the area had been carefully shaved to visualize the wound margin and for better visualization of epithelialization and granulation tissue area.

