7.7 Handling of Missing Data

All available data will be displayed and utilized in data analysis. Under the ITT principle, the subject will be considered as “non-healing” if no available data for post-baseline wound/ulcer healing assessment. Otherwise, the method of last observation carry forward (LOCF) will be used to account for incomplete observation.

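### Time to healing censors every non-healer at the last evaluation, with no Week 16 cut-off and no specific rule for lack-of-efficacy stops, so the curve and log-rank test depend on how other sections are read

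*Combined protocol and SAP*

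**What the plan says.** Section 7.4.2 starts the clock at first application of study treatment, takes the first observed healing as the event, and promises a Kaplan-Meier median and a log-rank test. Its censoring rule is: "Subjects who could not achieve complete ulcer healing at the last evaluation time point will be censored (non-healing) at the date of last evaluation". The 16-week limit appears in the objective (2.1), the primary variable (2.3.1) and the treatment duration (2.2.1, 5.2.1), but not in this rule.

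Three sets of passages bear on which date is the last evaluation.

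- **Exit.** Section 5.4 schedules wound measurement until confirmed closure "or until the study subject exited the study as lack of efficacy satisfactory". Section 5.2.1 defines that lack of efficacy as worsening to Wagner grade 3.
- **Follow-up.** Section 2.2.1 also mentions exit for failure, then continues: "treatment failure. After that, all subjects regardless of wound healing at the end of comparison period will be followed for 12 weeks". Section 3.4 defines discontinuation as early termination of study treatment, lists Wagner grade 3 worsening among the criteria, and asks for a withdrawal date and end-of-trial procedures. Section 5.1.4 schedules ulcer assessment and photography through Visit 14 (Week 28), with the instruction "Apply Aquacel® Hydrofiber® dressing to the subjects whose wounds are unhealed or recurrent".
- **Visit 10.** The footnote to the schedule of assessments says "Visit 10 indicates as the end of study treatment or prematurely discontinuation of study treatment". In Section 5.1.3, after early healing, study treatment "will be stopped at next scheduled visit which will be deemed as V10".

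For missing data, Section 7.7 treats subjects with no post-baseline healing assessment as non-healing; otherwise "the method of last observation carry forward (LOCF) will be used to account for incomplete observation". Section 7.2 leaves statistical detail to a separate SAP.

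**The concern.** Kaplan-Meier estimation assumes that a censored subject would have gone on to heal at the same rate as those still at risk. A subject whose ulcer has just worsened to Wagner grade 3 is a poor fit to that assumption. Censoring such subjects at exit removes likely non-healers from the risk set and pushes the healing curve up. The primary endpoint, through LOCF, keeps the same subjects as non-healers, so two analyses in one report could give different Week 16 healing rates.

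The missing cut-off is a second matter. It does not alter the curve before Week 16. It decides whether events in Weeks 18 to 28 enter the medians and the log-rank test, at a time when unhealed wounds in both arms are on the comparator dressing. Two competent analysts could follow 7.4.2 and report different results for the first-listed secondary efficacy endpoint.

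**Working it through.** **Inputs.** The plan gives no figure for this endpoint to reproduce. From Section 7.1: healing of 50% vs 30% within 16 weeks, and 118 per arm (212/0.90 = 235.6, rounded up to 236). Visits are every 2 weeks, with Week 16 at Day 113 ± 4. The documents give no exit rate and no follow-up healing rate, so these are assumptions shown as ranges. Healing is spread evenly over the eight visits at Weeks 2 to 16, and exits are drawn from subjects who would not heal.

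**1. Failures leave and are censored at exit.** The large-sample Week 16 estimate is 1 − Π(1 − d/n_k). Here d = p/8 is the share healing at each visit and n_k is the share still at risk, after removing those already healed or exited. For p = 40% and 10% exits spread over Weeks 2 to 8, d = 0.05 and n_k = 1.000, 0.925, 0.850, 0.775, 0.700, 0.650, 0.600, 0.550. The product is 0.565, so 40% reads as 43.5%. The upper limit, with every exit before any healing, is p/(1 − f) = 0.40/0.90 = 44.4%.

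The ranges below cover exits at Weeks 2–8, 2–16 and 8–14:

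| True healing | 5% exits | 10% exits |
|---|---|---|
| 30% | 30.6–31.2% | 31.3–32.5% |
| 40% | 40.9–41.7% | 41.9–43.5% |
| 50% | 51.2–52.2% | 52.6–54.6% |

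**2. Failures are followed for 12 weeks, stay unhealed, and the analysis stops at Week 16.** Only exits before Week 4 run out of follow-up before Week 16 (for example, 2 + 12 = 14). A true 40% reads as 40.0 to 40.2%.

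**3. No cut-off, so evaluation runs to Week 28.** Assume that the planned control rate continues unchanged on the comparator dressing. The share of unhealed ulcers closing in the 12 follow-up weeks is then 1 − 0.70^(12/16) = 23.5%.

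- ON101: 0.50 + 0.50 × 0.235 = 61.8%
- Control: 0.30 + 0.70 × 0.235 = 46.5%
- The difference shrinks from 20 to 15.3 points.
- About 118 × 0.50 × 0.235 = 13.9 of roughly 73 ON101 events fall after Week 16.

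In simulation, two-sided 5% log-rank power is about 88% at Week 16 and about 77% at Week 28. If 10% or 40% of unhealed ulcers closed in follow-up, power would be 83% or 70%. At 30% healing the control median is essentially never reached by Week 16. With follow-up counted, and 0 to 20% exits assumed, it is reached in 22 to 46% of runs.

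**4. Log-rank error, equal 40% healing, failures censored at exit.** Two-sided rejection stays close to 5% with equal exits. It is about 4 to 6% with 10% vs 5% exits.

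**5. The cut-off date.** Day 113 + 4 = Day 117 keeps every in-window Week 16 closure. A hard stop at Day 113, with visits spread evenly over the nine-day window, would lose 0.40 × 1/8 × 4/9 = 2.2 points at 40% healing.

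**The case against.** The strongest reply is that the plan is less open than it looks. Four parts of it stand.

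- **A rule exists.** A reader might infer that failures have no rule at all. They do: the sentence in 7.4.2 covers every non-healer. What is missing is a failure-specific rule and a defined date.
- **Week 28 is not the natural reading.** Section 1.4 promises 16 weeks of healing data, Section 2.1 sets a 16-week objective, and Section 7.4.3 uses follow-up only for recurrence in healed subjects. The two-weekly measurements of Section 5.4 do not fit visits at Weeks 20, 24 and 28. The drop in power is therefore what the literal wording permits, not what the plan most probably intends.
- **Follow-up of failures is well supported.** Sections 2.2.1 and 3.4 and the Visit 10 footnote favour it, and the bias is then negligible. They do not remove the exit wording in 5.2.1 and 5.4.
- **Crude rates will be visible.** Section 7.4.1 summarises healing percentages by visit, so an inflated curve could be noticed.

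A reader might also infer a raised false-positive risk for ON101. One-sided rejection does reach 3.3 to 4.3% against 2.5%, but only if ON101 is assumed to have 10% exits and control 5%. Nothing in the documents suggests that imbalance, and the opposite tail largely offsets it in the planned two-sided comparison.

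Finally, the separate SAP may already contain the rule.

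**Conclusion.** The point holds as a weakness of a secondary analysis. On the wording of 7.4.2, the result depends on passages that disagree about whether failures leave or are followed, and on a cut-off that is implied elsewhere but not stated.

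Its size rests on assumed exit and follow-up healing rates. It ranges from close to nil (failures followed, stop at Week 16), through the upward shifts in the table (failures censored at exit), to about 11 points of lost power (literal Week 28 reading, the least likely).

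It would be wrong to infer that the superiority conclusion is at risk. That conclusion rests on the logistic regression of the binary primary endpoint in Section 7.4.1, which this censoring rule does not touch.

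**What to change.** In Section 7.4.2:

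1. Set the cut-off by study day, at the end of the Week 16 window (Day 117). The Visit 10 label cannot serve, because it also marks early discontinuation and the visit after early healing.
2. Keep subjects who stop for lack of efficacy at risk as unhealed to Day 117.
3. Censor only other losses, at their last evaluation on or before Day 117.
4. State whether a first closure at Week 16 that is confirmed at the next visit counts as an event, and apply the same rule to the primary endpoint. Section 2.3.1 defines that endpoint as the "comparison of the incidence of complete healing of the target ulcer between the two treatment groups at the end of treatment", with healing maintained for at least 2 weeks, and does not settle this case.
5. Keep the current rule as a sensitivity analysis.

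Separately, the schedule footnote and Sections 2.2.1, 3.4, 5.1.3, 5.1.4, 5.2.1 and 5.4 must be reconciled on whether failures exit the study or are followed. The statistical rule above can be applied under either answer.

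The first interim analysis has been done (7.6.2), so the cost is a documented amendment (8.3.3) before the next look. Reported healing fractions may be slightly lower, and there is one extra sensitivity row. No new data are needed. If the separate SAP already sets these rules, copying them into 7.4.2 closes the analysis part of the point.
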